3.3. Stopping Criteria

3.3.1. Individual Stopping Criteria^a

In this phase 2a safety study, the following individual stopping rules will apply:

The investigator or sponsor believes (e.g. that for safety or tolerability reasons such as a serious adverse event at least possibly related to the study drug) it is in the best interest of the subject to discontinue the study.

The subject becomes pregnant

A subject will be discontinued from the study when the QTc interval (QTcF; QTcB if ECG machine only shows QTcB) is higher than 500 msec. ECG events should be confirmed by repeat twice as soon as possible after the initial ECG, and the average value of the QTcB interval will be used to determine whether a subject should be discontinued. The subject will continue to be monitored by repeated 12-lead ECGs (at least every 60 min) until the ECG normalizes.

Because of limited information on the effects of JNJ-42165279 on the human liver function a subject will be discontinued from the study if either of the following occur:

- Aspartate transaminase (AST) and/or alanine transaminase (ALT) >3 x ULN (confirmed by repeat),
- Total bilirubin >2 x ULN (confirmed by repeat).

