11.3. Safety Analysis^a

All subjects receiving at least one dose of study drug will be included in the safety analysis. All safety analyses will be performed based on the safety analysis set, which will include all randomized subjects who receive at least 1 dose of study drug.

Adverse Events

The verbatim terms used in the CRF by investigators to identify adverse events will be coded using the Medical Dictionary for Regulatory Activities (MedDRA). All reported adverse events with onset during the double-blind treatment phase (i.e., treatment-emergent adverse events, and adverse events that have worsened since baseline) will be included in the analysis. For each adverse event, the percentage of subjects who experience at least one occurrence of the given event will be summarized by treatment group. Summaries will be provided for all subjects receiving at least one dose of study drug in this study, and will include adverse events from this study.

Summaries, listings, datasets, or subject narratives may be provided, as appropriate, for those subjects who die, who withdraw due to an adverse event, or who experience a severe or a serious adverse event.

Clinical Laboratory Tests

Laboratory data will be summarized by type of laboratory test. Descriptive statistics will be calculated for each laboratory analyte at baseline and at each scheduled time point, and for changes from baseline.

The number and percentage of subjects experiencing a laboratory result below or above normal reference ranges will be provided for each laboratory analyte by treatment group. Summaries will be provided for all subjects receiving at least one dose of study drug in this study.

A listing of subjects with any laboratory result outside the reference ranges will be provided.

12-Lead ECG

Heart rate and ECG intervals (RR, PR, QRS and QT) as well as corrected QT intervals according to Bazett's formula (QTcB) and Fridericia's formula (QTcF) from the 12-lead ECG will be summarized at baseline and at each scheduled time point and for changes from baseline using descriptive statistics.

The number and percentage of subjects with at least one occurrence of a treatment-emergent potentially clinically important QTc measurement (QTc value >450, >480, or >500 msec) or with a change from baseline in QTc >30 msec will be summarized by treatment group.

^a This section has been amended per Amendment INT-2.

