### 2.4. Analysis Timepoints and Phases

Please refer to the time and events schedule in the latest version of the protocol for analysis timepoints per assessment.

**Baseline (reference time point):** for each of the Lead-in, DB Treatment and Withdrawal Period, the reference assessment, i.e. baseline, is the measurement the closest, and prior to the first study medication administration of that period. The baseline measurement may be taken from a scheduled or unscheduled visit.

**End Point for double-blind treatment period:** end point is defined as the last non-missing post-baseline observation during the double-blind treatment period. End point will be defined only for the double-blind treatment period.

Analysis phases will be constructed as follows:

Analysis Phase	Start Date/time	End Date/time
Screening	00:00 of the date of signing the informed consent	1 minute before the first study medication administration in the Lead-in Period
Lead-in Treatment Period	Date/time of the first study medication administration in the Lead-in Treatment Period	1 minute before the first study medication administration in the Double-Blind Treatment Period

		If the subject does not enter the Double-blind Treatment Period then use 23:59 of the day before the date of the first Follow-Up visit
Double-Blind Treatment Period	Date/time of the first study medication administration in the Double-Blind Treatment Period  If the subject takes the morning dose on the day of randomization prior to the randomization (i.e. a dose of the lead-in medication), the time of morning intake of the next day is not known. The start date of the double-blind treatment period will be the day after the day of randomization, and the time of intake will be imputed as 0:00.	1 minute before the first study medication administration in the Withdrawal Treatment Period.  If the subject does not enter the Withdrawal Treatment Period then use 23:59 of the day before the start of the Follow-Up period.
Withdrawal Treatment Period	Date/time of the first study medication administration in the Withdrawal Period	Day 77 visit or early withdrawal visit for subjects who dropout early.
Follow-up	00:00 of the date after the Day 77 visit or early withdrawal visit for subjects who dropout early.	23:59 of the day of study termination (date of last contact)

The last phase, whichever it is for a subject, always ends on 23:59 of the day of study termination (last contact).

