## 2.5. Visit Windows

As subjects do not always adhere to the protocol visit schedule, the following rules are applied to assign actual visits to analysis visits. Listed in Table 1 are visit windows and the target days for each visit. The reference day is Study Day 1 for each of the lead-in, the double-blind treatment and the withdrawal period.

If a subject has 2 or more actual visits in one visit window, the visit closest to the target day will be used as the protocol visit for that visit window. The other additional visit(s) will not be used in the summaries or analyses. If 2 actual visits are equidistant from the target day within a visit

window, the later visit is used. If a visit window has no scheduled visits but does have unscheduled visits, then the unscheduled visit closest to the scheduled visit will be used.

All assignments will be made in chronological order. Once a visit date is assigned to a visit window, it will no longer be used for a later time point except for the endpoint. Listed below (Table 1) are the visit windows and the target days (if applicable) for each visit defined in the protocol.

Table 1 – Visit Windows

Parameter	Scheduled Visit Number	Time Interval (label on output)	Time Interval (Day) 	Target Time Point (Day) by Period	Analysis Phase
HDRS 17 , C-SSRS	1	Screening	< 1	-28 to -1	Screening
	2	Lead-in Baseline	<=1	1	Lead-in
	3	Lead-in Week 1	2 to 10	7	Lead-in
	4	Lead-in Week 2	11 to 17	14	Lead-in
	5	Lead-in Week 3	18 to 24	21	Lead-in
	5	DB Treatment Baseline	<=1	1	DB Treatment
	6	DB Treatment Week 1	2 to 10	7	DB Treatment
	7	DB Treatment Week 2	11 to 21	14	DB Treatment
	8	DB Treatment Week 4	22 to 35	28	DB Treatment
	9	DB Treatment Week 6	36 to 49	42	DB Treatment
		DB Treatment End Point 			DB Treatment
	9	Withdrawal Baseline	<=1	1	Withdrawal
	10	Withdrawal Week 2	2 to 20	14	Withdrawal
CPFQ, CUDOS-A, SHAPS, MOS Sleep-R, PSS	2	Lead-in Baseline	<=1	1	Lead-in
	3	Lead-in Week 1	2 to 14	7	Lead-in
	5	Lead-in Week 3	15 to 28	21	Lead-in
	5	DB Treatment Baseline	<=1	1	DB Treatment
	7	DB Treatment Week 2	2 to 21	14	DB Treatment
	8	DB Treatment Week 4	22 to 35	28	DB Treatment
	9	DB Treatment Week 6	36 to 49	42	DB Treatment
			DB Treatment End Point 		
	9	Withdrawal Baseline	<=1	1	Withdrawal
	10	Withdrawal Week 2	2 to 20	14	Withdrawal
SATE	10	Withdrawal Week 2	2 to 20	14	Withdrawal
SIGH-A	2	Lead-in Baseline	<=1	1	Lead-in
	3	Lead-in Week 1	2 to 10	7	Lead-in

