### 5.3. Clinical Laboratory Tests

For each study period, descriptive statistics on actual values and changes from respective period baseline at each scheduled time point for hematology, chemistry, urinalysis and coagulation will be provided for the Safety analysis set. Laboratory summaries will be provided in Standard International (SI) units. All laboratory data will be listed for the All Subjects set.

Cross-tabulations (with classes for below, within, and above the central laboratory range) showing the shift of laboratory values from baseline to each scheduled time point and endpoint will be presented by treatment group and study period.

Clinical laboratory test values will be considered “treatment emergent markedly abnormal” (TEMA) using the criteria defined by the Sponsor (Johnson & Johnson Research & Development, LLC) listed in Table 3. The identification of TEMA laboratory values is based on baseline value (in any period) being missing or within the normal range and the corresponding post baseline value being markedly high/low as per the values in Table 3. If post baseline laboratory results are above the upper limit and the baseline value is below the lower limit, then the post baseline abnormality will also be considered TEMA. The same applies to the post baseline value being below the lower limit with the baseline value being above the upper limit.

The incidence of TEMA will be presented by treatment group and study period at each scheduled time point and endpoint.

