### Suicidal Behavior (6-10)

- 6: Preparatory acts or behavior
- 7: Aborted attempt
- 8: Interrupted attempt
- 9: Non-fatal suicide attempt
- 10: Completed suicide

A frequency distribution at each scheduled time point and endpoint will be provided by treatment group and study period. A listing will be provided of C-SSRS items throughout the study for subjects with suicidal ideation or behavior at any time point.

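### The one-visit-per-window rule in SAP 2.5 has no safety exception, so an abnormal value at an additional visit can be missing from every by-arm laboratory, vital-sign or C-SSRS value table

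*SAP*

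**What the plan says.** SAP 2.5 chooses one record: "If a subject has 2 or more actual visits in one visit window, the visit closest to the target day will be used". Ties go to the later visit. The others are excluded: "The other additional visit(s) will not be used in the summaries or analyses". Table 1 puts C-SSRS, vital signs, laboratory tests and 12-lead ECG under this rule together with the efficacy scales.

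An additional visit can still be used in some cases. One is an otherwise empty window: "If a visit window has no scheduled visits but does have unscheduled visits, then the unscheduled visit closest to the scheduled visit will be used". Another is End Point; in SAP 2.4, "end point is defined as the last non-missing post-baseline observation during the double-blind treatment period". End Point exists for the double-blind period only. An unscheduled visit may also supply a period baseline.

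The by-arm safety tables in SAP Section 5 mostly follow the visit schedule:

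- Laboratory (5.3): "The incidence of TEMA will be presented by treatment group and study period at each scheduled time point and endpoint". The count of liver tests above normal has the same structure.
- Vital signs (5.4): treatment-emergent abnormalities are by scheduled time point and endpoint.
- C-SSRS (5.6): "A frequency distribution at each scheduled time point and endpoint will be provided by treatment group and study period".
- ECG (5.5) differs: subjects with abnormal values are counted by arm and study period, and QTc categories are tabulated over time.

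None of these sections defines a worst or any-time value taken from all records. Protocol 11.3 plans, by arm, "The number and percentage of subjects with at least one occurrence of a treatment-emergent potentially clinically important QTc measurement".

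The protocol expects extra measurements. Section 9.1.1 allows them after abnormal safety findings. Section 3.3.1 calls for a confirming repeat of raised AST/ALT or bilirubin, and for ECG says "ECG events should be confirmed by repeat twice as soon as possible after the initial ECG".

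**The concern.** Keeping one record per window is sound for means by visit, where each subject should count once. It does not suit an incidence table, which asks whether an abnormality occurred at all. Under the rule as worded, whether an abnormal value is counted depends on how near its date lies to a target day.

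Overall safety and tolerability is part of the primary objective. Protocol 16.1 describes a transaminase signal in an earlier multiple-dose study: 5 of 30 exposed subjects against 1 of 10 on placebo. The liver table is therefore one that readers will look at closely, and it should count every qualifying value.

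**Working it through.** The plan states no figure to reproduce. The check applies the selection rule to the Table 1 windows.

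**Inputs.** Double-blind windows for laboratory tests, ECG and vital signs: Days 2-21, 22-35 and 36-49, targets 14, 28 and 42 (20 + 14 + 14 = 48 days). For C-SSRS: Days 2-10, 11-21, 22-35 and 36-49, targets 7, 14, 28 and 42 (9 + 11 + 14 + 14 = 48 days). The protocol's visit allowance is 3 days either way.

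**Rule.** With target t and scheduled visit on day s, an additional visit on day u takes the window if |u - t| < |s - t|, or if the distances are equal and u > s. Otherwise it is dropped.

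**Days on which an additional visit is dropped**

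| Scheduled visits | Laboratory, ECG, vital signs | C-SSRS |
|---|---|---|
| On target | 45 of 45 | 44 of 44 |
| 3 days early | 45 - 3 x 6 = 27 of 45 (60%) | 44 - 4 x 6 = 20 of 44 (45%) |
| 3 days late | 45 - 3 x 5 = 30 of 45 (67%) | 44 - 4 x 5 = 24 of 44 (55%) |

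With an early scheduled visit, the additional visit wins on the 6 days from t - 2 to t + 3. With a late one, it wins on the 5 days from t - 2 to t + 2. These counts describe the rule; they are not estimates of how often values will be lost. A dropped visit can still supply End Point if it is the last in the double-blind period.

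**ALT example (invented values, normal baseline).** Window Days 22-35, target 28.

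- Scheduled Day 28, 2.6 x ULN: distance 0, kept for Week 4.
- Unscheduled Day 31, 4.2 x ULN: distance 3, dropped.
- Early withdrawal Day 34, 2.9 x ULN: distance 6, dropped from the window. Under SAP 2.4 follow-up starts the day after the early-withdrawal visit, so Day 34 is still double-blind and supplies End Point.

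The Week 4 row uses 2.6 and the End Point row uses 2.9. SAP Table 3 sets the ALT limit at >3 x ULN, so no TEMA is counted although 4.2 was observed. The subject is counted as above normal, because 2.6 and 2.9 both exceed the ULN.

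**C-SSRS example (invented values).** Window Days 11-21, target 14. Day 14 scores 0 (distance 0, kept), and unscheduled Day 18 shows ideation score 4 (distance 4, dropped). Day 28 scores 0 on the form covering the time since the last visit. If Day 18 is not the last double-blind assessment, the score of 4 enters no row of the by-arm C-SSRS table.

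**ECG.** A count by arm and period in SAP 5.5 could mean any occurrence, as in Protocol 11.3. But SAP 2.5 excludes the unselected visits from all summaries, and 5.5 does not override it. The protocol's count is therefore not assured.

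**The case against.** The strongest reply is that little of clinical weight would be hidden. Protocol 9.2 requires clinically relevant changes to be recorded as adverse events, Attachment 11 names suicidal ideation and behaviour among the events captured, and the by-arm adverse event tables in SAP 5.2 are not windowed. All safety data are listed, liver results are plotted per subject, and SAP 5.6 lists C-SSRS items for any subject with ideation or behaviour. This stands, and it rules out saying that such values reach no by-arm table at all. But an adverse event table shows an event that an investigator chose to report, not a count of values beyond a fixed limit, and listings give no incidence by arm.

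A reader might also infer more than the documents support:

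- That repeats are always lost. A confirming repeat often follows a retained abnormal value, which is already counted. SAP 2.5 selects among visits and is silent on repeats within one visit.
- That the ALT example meets the protocol's stopping criterion. That criterion needs confirmation by repeat, and the next value is 2.9. The example shows only a missed TEMA.
- That the C-SSRS loss is certain. Nothing requires a C-SSRS at an unscheduled visit, persisting ideation can be rated again later, and a last double-blind assessment feeds End Point. A dropped rating need not reappear; that is all that follows.
- That SAP 5.5 contradicts Protocol 11.3. It does so only if the 2.5 exclusion is read into it.
- That one arm is favoured. No rate of unscheduled visits by arm is documented.

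**Conclusion.** The point holds as a statement of what can happen. An abnormal value at an additional visit can be missing from every by-arm laboratory, vital-sign or C-SSRS value table, unless that visit is closest to target, is the only one in its window, or gives the last double-blind value. For ECG the wording leaves the any-occurrence QTc count unassured.

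This is a stated rule that can give too low a count of subjects with an abnormality, and not merely a missing detail. It rests on reading the SAP 2.5 exclusion literally, as covering safety summaries; nothing in Section 5 says otherwise. How often it would change a table, and whether it would affect one arm more than the other, cannot be determined from the documents.

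**What to change.** In SAP 2.5, limit the one-visit-per-window rule to by-visit descriptive statistics and efficacy analyses. In SAP 5.3 to 5.6, base the incidence of abnormalities (TEMA, liver tests, vital signs, ECG and QTc, C-SSRS) on all post-baseline records in the period, including unscheduled, repeat and early-withdrawal records. Add one any-time-in-period (worst value) row per arm and period. This also secures the QTc count planned in Protocol 11.3.

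The cost is SAP wording and one extra row per table. No new data are needed and the efficacy analyses are unchanged. Reported incidences may be slightly higher.

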### 3. SUBJECT INFORMATION

Subject information will be summarized for the Safety Analysis Set and listings will be created for the All Subjects Set.

#### 3.1. Demographics and Baseline Characteristics

The following demographic and baseline characteristics variables will be listed and summarized by treatment group and overall:

- age at screening (years)
- sex
- race and ethnicity
- country
- lead-in response status
- height at baseline (cm)
- weight at baseline (kg)
- BMI at baseline ( $\text{kg}/\text{m}^2$ )  $\text{baseline weight (kg)} / (\text{baseline height (m)})^2$
- duration of prior antidepressant treatment (in days)

Baseline disease characteristics will be summarized at lead-in baseline and at double-blind treatment baseline for the following assessments: HDRS17 total score, SIGH-A total score, HAM-A6 subscale score, HAM-D6 subscale score and HDRS17 anxiety/somatization factor score.

The summary of demographic and baseline characteristics and baseline disease characteristics will be presented for the Safety analysis set, the Enriched Safety analysis set, the Enriched ITT set and the Full ITT set. In addition, the summary for the Safety analysis set will be presented by country and by enrollment prior to/after study suspension.

The following screening and/or pre-dosing test results will be listed:

- urine drug screen abnormalities
- positive serology results
- serum FSH results that are  $\leq 40$  IU/L (females only)
- positive alcohol results

If no abnormalities or positive results, an empty listing will be produced stating “No data to report”. If a subject has an abnormal finding, all related results will be listed (e.g. all serology results, or all drug screening results).

All medical history data will be presented in a listed.

Results from the Mini-international neuropsychiatric interview (MINI) will be listed.

#### 3.2. Disposition Information

The number of subjects in each analysis set will be presented, and the number of subjects by country and center will be presented for the Safety analysis set and for the Enriched ITT set.

Study completion/withdrawal information will be summarized by treatment group and overall and will be listed. The distribution of study termination reasons will also be summarized.

The distribution of time to study discontinuation will be presented graphically using Kaplan-Meier estimates. The time to discontinuation will be calculated as the duration (in days) from Study Day 1 of the lead-in period (defined in Section 2.4) to study discontinuation. Subjects who complete the study will be censored at the study disposition date.

Study completion and withdrawal information will be presented for the Safety analysis set and the Enriched ITT set and the information for each subject will also be presented in a listing.

The number and percentage of subjects who enter lead-in period, the double-blind treatment period and the withdrawal period and who complete the lead-in period, the double-blind treatment period and the withdrawal period will be summarized.

The number and percentage of lead-in placebo responders will be summarized overall, by country and by site. A cumulative distribution plot of the percent reduction in HDRS17 total score from lead-in baseline at the end of the lead-in period will be provided overall and by country. To explore the duration of response for lead-in placebo responders, a Kaplan-Meier plot will be presented for the distribution of time to worsening (i.e. no longer meeting  $\geq 40\%$  improvement) after the lead-in period. Time to worsening will be calculated as the duration (in days) from Study Day 1 of the double-blind treatment period (defined in Section 2.4) to the first visit where  $< 40\%$  improvement in HDRS17 total score is observed. Subjects who do not reach the worsening criterion will be censored at the study disposition date.

### **3.3. Treatment Compliance**

The number of tablets dispensed and returned at each visit will be listed.

### **3.4. Extent of Exposure**

Study drug administration information will be presented for each subject in a data listing.

Treatment duration is defined as the number of days between the first and last day of study drug in the treatment phase (including lead-in, double-blind treatment and withdrawal): last day of study drug administration – first day of study drug administration + 1.

Descriptive statistics of treatment duration will be presented. A frequency distribution for the treatment period only will also be provided using the following categories:  $< 1$  week ( $< 7$  days), 1- $< 2$  weeks (7- $< 14$  days), 2- $< 3$  weeks (14- $< 21$  days), 3- $< 5$  weeks (21- $< 35$  days), 5- $< 7$  weeks (35- $< 49$  days), 7- $< 9$  weeks (49- $< 63$  days), 9- $< 11$  weeks (63- $< 77$  days) and  $\geq 11$  weeks ( $\geq 77$  days).

### 3.5. Protocol Deviations

All major protocol deviations will be listed.

### 3.6. Prior and Concomitant Medications

Prior therapies and concomitant medications (relative to the double-blind treatment period) will be tabulated in 3 separate summaries:

1. **Prior medication** – any medication which starts and ends before the date/time of first study drug administration in the Double-blind Treatment Period
2. **Prior and concomitant medication** – any medication which starts before the date/time of first study drug administration in the Double-blind Treatment Period and ends after the date/time of first study drug administration in the Double-blind Treatment Period
3. **Concomitant medication** – any medication which starts after the date/time of first study drug administration in the Double-blind Treatment Period

If a prior or concomitant therapy record is missing components of its start and/or stop dates (day and/or month and/or year) then missing data will not be imputed, however, the following approaches will apply:

- If the start year is the same as the year of first drug administration but the start day and month is missing, the medication will be considered as having started before the study.
- If the start month and year is the same as the month and year of first drug administration but the start day is missing, the medication will be considered as having started before the study.
- In case of a completely missing start date, the medication will be considered as having started before the study.
- If the end year is the same as the year of last drug administration but the end day and month is missing, the medication will be considered as ongoing at the end of the study.
- If the end month and year is the same as the month and year of first drug administration but the end day is missing, the medication will be considered as ongoing at the end of the study.
- In case of a completely missing end date, the medication will be considered as ongoing at the end of the study.

In addition, the following will also be listed:

- preplanned surgery/procedures
- antidepressant Treatment History Questionnaire (ATRQ) – any medication that is recorded on the ATRQ form

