## 1.2. Trial Design

This is a multi-center, double-blind, placebo-controlled, randomized, parallel-group study in subjects with MDD with anxious distress who have had inadequate response to SSRI/SNRI treatment.

Subjects who meet the inclusion and exclusion criteria and are enrolled will be maintained on the SSRI/SNRI treatment throughout the study to determine whether adjunctive treatment with JNJ-42165279 can reduce symptoms of MDD with anxious distress.

[figure not shown]
For each subject, the study will consist of three phases: a screening phase of up to 4 weeks, a treatment phase lasting up to 11 weeks, and a 3-week post-treatment (follow up) phase. The treatment phase of the trial will consist of 3 periods. The first period is a placebo lead-in of 3 weeks for all subjects, after which subjects will enter the double-blind treatment period when they will be randomly assigned to JNJ-42165279 or continuation on placebo for 6 weeks. Subjects who successfully complete the double-blind treatment period will be treated with placebo during a 2-week withdrawal period. The total study duration for each subject will be approximately 18 weeks.

The end of study is defined as the date of the last visit of the last subject undergoing the trial. Investigators and subjects will remain blinded to the exact duration of the subject lead-in and withdrawal period during the entire study duration.

Approximately 143 subjects will enter the double-blind placebo lead-in period. At the end of the lead-in period, response status of the subjects will be assessed according to the double-blind response criteria based on reduction in HDRS17 relative to lead-in baseline. Both lead-in placebo responders and lead-in placebo non-responders will be randomly assigned in a 1:1 ratio to either 25 mg of JNJ-42165279 or placebo in the treatment period. The primary efficacy analyses will be based on the treatment period data from the lead-in non-responders (94 subjects).

An overall flow diagram of the study is shown in the figure below.

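### SAP 3.6: the month-level stop-date rule and the open-ended third category can put medications in the wrong descriptive table

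*SAP*

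**What the plan says.** SAP 3.6 plans three medication tables, described as relative to the double-blind period:

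- *Prior*: "any medication which starts and ends before the date/time of first study drug administration in the Double-blind Treatment Period".
- *Prior and concomitant*: started before that dose and ended after it.
- *Concomitant*: "any medication which starts after the date/time of first study drug administration in the Double-blind Treatment Period".

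The section says missing date parts are not imputed, then gives six bullets for incomplete dates. Three concern end dates:

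- Year only: "If the end year is the same as the year of last drug administration but the end day and month is missing".
- Month and year: "If the end month and year is the same as the month and year of first drug administration but the end day is missing".
- End date completely missing.

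All three end the same way: "the medication will be considered as ongoing at the end of the study". The matching start-date bullet reads "If the start month and year is the same as the month and year of first drug administration but the start day is missing", and its result is that the drug started before the study.

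No bullet says which first administration is meant. The three table definitions use the first double-blind dose. SAP 3.4 counts treatment duration from the first study drug with the lead-in included.

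On timing, SAP 1.2 describes "a treatment phase lasting up to 11 weeks" and states: "The first period is a placebo lead-in of 3 weeks for all subjects". Protocol Section 8 has therapies recorded from 30 days before screening to the follow-up visit.

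**The concern.** Two neighbouring end-date bullets share an outcome but use different anchors, with no explanation. The month-level bullet has the same anchor as the start-date bullets, which suggests a carry-over in drafting. That the last dose was intended is an inference, but the year-level bullet supports it.

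The written rule also overrides data. A year-only stop date leaves room for a drug to be ongoing; a recorded stop month equal to the month of the first dose does not. The bullets compound: a short course whose start and stop are both recorded only as the month of the first dose becomes one that began before the study and lasted to its end.

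The third table has a lower limit but no upper one, although the SAP defines separate withdrawal and follow-up phases.

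At stake is the by-arm description of co-medication during randomised treatment. It could include drugs that had already stopped, and drugs begun only after subjects in both arms were back on placebo.

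**Working it through.** **Inputs.** Lead-in 3 weeks, double-blind period 6 weeks, withdrawal 2 weeks (SAP 1.2). Visit 6 is Day 28 in the Protocol's Time and Events Schedule and double-blind Day 7 in SAP Table 1, so double-blind Day 1 is study Day 22. On the same basis the double-blind period ends on Day 63 and withdrawal on Day 77. Follow-up falls on Day 84 to Day 98. The documents give no figure of their own to reproduce here.

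**1. Where the end date matters.** The only cut-point for an end date is the first double-blind dose, and it separates *prior* from *prior and concomitant*. *Concomitant* depends on the start date alone.

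**2. Can the month-level bullet act as a last-dose rule?** Day 22 to Day 63 is 41 days and Day 1 to Day 77 is 76 days. Both exceed the longest month, so for a completer the first-dose and last-dose months never coincide. Enumerating 730 start dates (2017–2018, an assumed range) gave 0 coincidences. As written, the bullet never reaches a completer's last-dose month.

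**3. If the first dose is the lead-in dose.** Let Day 1 be day d of a month with L days. Day 22 is d + 21, which falls in the next month when d + 21 > L. That holds for d = L − 20 to L, which is 21 start days in every month. Over a year: 21 × 12 = 252, and 252 / 365 = 69%. For those start dates, any drug stopped in the Day 1 month had ended before double-blind dosing and is certainly *prior*. The bullet makes it ongoing, so it is tabulated as *prior and concomitant*. Example: Day 1 on 20 March puts the first double-blind dose on 10 April. A stop recorded as March with no day was over at least 10 days earlier, yet the drug is carried to study end.

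If the first double-blind dose is taken on Day 21 itself, the count is 20 start days a month: 240 / 365 = 66%.

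**4. If the first dose is the double-blind dose.** A stop in that month with the day missing may fall on either side of the cut-point. If the stop day is uniform over the month (an assumption), about 48% precede the dose. *Prior and concomitant* is then a cautious class. Ongoing to study end still contradicts the recorded stop month.

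**5. The third category.** Double-blind starts run from Day 22 to Day 63, 42 days. Recording continues to the follow-up visit:

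- Visit on Day 84: 84 − 63 = 21 extra days, so 21 of 63 days of eligible start dates (33%) lie after the double-blind period.
- Visit on Day 98: 98 − 63 = 35 extra days, so 35 of 77 (45%).

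These are shares of calendar time, not of records. For adverse events, SAP 5.2 reports onsets more than 4 days beyond double-blind treatment separately. SAP 3.6 has no counterpart for medications.

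**The case against.** The strongest reply is that the bullets serve only to sort records, and that the first-dose month is exactly where sorting is uncertain. Read with the double-blind dose as anchor, the month-level bullet addresses the one ambiguous month and errs on the cautious side. A stop in a completer's last-dose month needs no rule for this purpose, because it is already after the cut-point. This stands, and it means that merely replacing the first dose by the last would leave the ambiguous month without a rule. It does not rescue the lead-in reading, which the text allows, or the claim that the drug is ongoing at study end.

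Three stronger readings are tempting, and the documents do not support them.

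- *Weeks of spurious exposure.* A reader might infer up to about 14 weeks (Day 1 to Day 98) of invented exposure per record. SAP 3.6 imputes no dates and plans no duration of co-medication, so that quantity is never derived. Nor is every affected record misclassified: with Day 1 on 5 March, the double-blind dose is on 26 March, and a stop in March may fall on either side of it.
- *Mostly prohibited drugs.* Nothing shows this. Benzodiazepines are barred from 7 days before screening (Protocol Section 8), and CYP3A4 inhibitors or inducers must stop at least 5 half-lives before Day 1 (Protocol 4.2), so many compliant stops would precede the relevant month.
- *False protocol deviations.* SAP 3.5 only lists major deviations, and nothing derives them from these tables. An effect on the per-protocol set is therefore not shown.

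It can also be said that the open third category is a matter of presentation. In part it is, but the section itself ties the tables to the double-blind period.

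**Conclusion.** The point holds as a minor one. SAP 3.6 has two rules that can place medications in the wrong table: a month-level stop rule with an inconsistent and undefined anchor, and a third category that runs past the double-blind period.

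If the first dose means the lead-in dose, the first rule misclassifies records with certainty for about 69% of start dates. That figure assumes the nominal schedule and start dates spread evenly over the year. It applies only to records with a stop month equal to the Day 1 month and no day. If the double-blind dose is meant, the class is defensible and only the ongoing label is wrong. The second rule admits starts from 21 to 35 days beyond Day 63.

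The number of affected records is not given and could be zero. The consequence is limited to descriptive medication tables. The MMRM, the analysis-set definitions and the type I error are unaffected.

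**What to change.** In SAP 3.6:

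1. State that the first drug administration means the first double-blind dose throughout.
2. Anchor the month-level ongoing bullet on the month of the last administration, in line with the year-level bullet.
3. Add that a stop in the month of the first double-blind dose with the day missing is classed as prior and concomitant, but not as ongoing to study end, and that a stop in an earlier month is prior.
4. Limit the third category to starts within the double-blind period, and show starts in withdrawal and follow-up separately.

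For an early dropout whose first double-blind and last doses fall in one month, items 2 and 3 both apply. The table is the same either way, but one clause should say which ongoing label takes precedence.

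The cost is a few lines of SAP text and a small programming change, with no new data to collect.
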